5.2.2 Objective response rate (ORR)

ORR will be assessed in the response evaluable analysis set (patients who undergo retreatment with durvalumab in Cohort 2). The ORR will be based on the site investigator RECIST 1.1 data and using all tumor assessments, regardless of whether they were scheduled or not. Descriptive statistics will be performed on the ORR and the following data will be presented: the number of observations, 95% (Confidence Interval) CIs estimated using the exact probability method. Data will be summarized by tumor type if there is sufficient sample size in each tumor type.

In case there is no sufficient sample size in retreated Cohort 2, the corresponding tables will be purely informative and only listings will be used for the assessment of this objective.

5.2.3 Duration of response (DOR)

DOR will be assessed in the response evaluable analysis set (patients who undergo retreatment with durvalumab in Cohort 2). KM plots of DOR based on the investigator assessment of RECIST will be presented. Median DOR (with associated 95% CI) will be calculated from the KM curve and summarized. Only patients who have a confirmed response will be included in this summary table. In addition, swimmer plots that show the profile of each patient who responds will also be produced.

Results will be summarized by tumor type if there is sufficient sample size in each tumor type.

In case there is no sufficient sample size in retreated Cohort 2, the corresponding tables and graphs will be purely informative and only listings will be used for the assessment of this objective.

5.2.4 Time to response (TTR)

Descriptive data will be provided for TTR in responding patients. In addition, KM plots of TTR will be produced where patients without a response will be censored at their last RECIST assessment. Median TTR (with associated 95% CI) will be calculated from the KM curve and summarized. Results will be summarized by tumor type if there is sufficient sample size in each tumor type.

In case there is no sufficient sample size in retreated Cohort 2, the corresponding tables and graphs will be purely informative and only listings will be used for the assessment of this objective.

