1.1 Schedule of activities

The SoA are based on Cohort entry type as part of the study design (Table 1 to Table 3).

Patients in Cohort 1 and those going onto durvalumab retreatment in Cohort 2 will receive durvalumab monotherapy by infusion every 4 weeks on Day 1 of each cycle. For all patients treated with durvalumab, cycle assessments will be completed every 4 weeks (± 3 days) until confirmed PD, unless unacceptable toxicity, withdrawal of consent, or another discontinuation criterion is met (Table 1 and Table 2). For the purposes of this study, "confirmed" PD is determined by the Investigator using RECIST v1.1 at least every 12 weeks while the patient remains on treatment according to standard clinical practice. There are no mandated confirmatory scans, unless the Investigator plans to treat the patient beyond PD. All assessments on treatment days are to be performed prior to durvalumab infusion, unless otherwise indicated. Prior to commencing infusion with durvalumab (within 3 days), the results for liver function tests, electrolytes, full blood count, and creatinine must be available and reviewed by the treating physician or Investigator. Patients will undergo various assessments for vital signs (including temperature, respiratory rate, blood pressure, body weight, and pulse), concomitant medication, laboratory, safety, adverse event/serious adverse event, and tumor assessments. Safety assessments will be performed according to the National Cancer Institute Common Terminology Criteria for Adverse Events v5.0. Any assessments which are relevant to preservation of patient safety, as scheduled in the parent clinical study, will be conducted and followed up as per the SoA for this study.

Upon discontinuation of durvalumab, for both Cohort 1 and among the patients who undergo retreatment in Cohort 2, follow-up will continue as per the SoA for Cohort 3 (Table 3). Only one course of retreatment is allowed (inclusive of any retreatment in the parent clinical study).

For patients receiving durvalumab monotherapy

- Patients may delay dosing under certain circumstances:
 - Dosing may be delayed per the Dosing Modification and Toxicity Management Guidelines, due to either an immune or a non-immune-related AE (Annex 1).
 - If dosing must be delayed for reasons other than treatment-related toxicity, dosing will resume as soon as feasible.

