Clinical chemistry ^h		X	X	X		X	X	X	X	X
Hematology ^h		X	X	X		X	X	X	X	X
TSH (reflex free T3 or free T4) ⁱ		X	X	X		X	X	X	X	X
Pregnancy test ^j		X				X	X	X	X	X

	Follow-up before retreatment				Retreatment					
	Time since the last dose of study drug ^a			Long-term follow-up	Baseline ^b / C1	C2	C3	C4	C5 onwards ^c	
Week	Baseline/ Enrollment ^a	Day (±3 days)	Day (±7 days)		Every 3 months (±2 weeks)	0	Q4W ±3 days unless dosing needs to be held for toxicity reasons			
Day		30	60	90		1	Q28days ±3 days unless dosing needs to be held for toxicity reasons			
Monitoring										
AE/SAE assessment ^k		X	X	X		Throughout				
Survival status ^l					X					
Study drug administration										
Durvalumab (monotherapy) ^m						X	X	X	X	
Tumor assessment										
Tumor assessment ⁿ	Assessment performed according to the Investigator’s standard practice until withdrawal of consent, progression or death.					X ^o	Assessment performed according to RECIST v1.1 as determined by the Investigator (at least every 12 weeks) until withdrawal of consent, progression or death.			

- a. Follow-up visits are performed based on the duration since the last dose of study drug in either the parent clinical study or current study (whichever most recently administered the study drug). Patients who are more than 90 days beyond the last dose of study drug, will not undergo follow-up for AEs/SAEs, vital signs, concomitant medications, or laboratory safety assessments; these patients will be followed for survival and undergo tumor assessment per Investigator’s standard practice.
- b. Baseline assessments may be performed over more than 1 visit if necessary. If laboratory or imaging procedures were performed for alternate reasons prior to signing the consent, these can be used for baseline assessment purposes with consent of the patient. However, all baseline laboratory assessments must be obtained within 3 days prior to Day 1 (first retreatment visit), and baseline imaging results must be obtained within 28 days prior to Day 1 of retreatment. Baseline laboratory assessments performed within 3 days prior to Day 1 do not need to be repeated at Day 1. Patients with documented HIV test results from the parent clinical study do not need to undergo a repeat test, but HBV and HCV must be retested within the 28-day period.

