3 PRIMARY AND SECONDARY VARIABLES

3.1 Efficacy variables

3.1.1 Objective response rate (ORR)

ORR is defined as the percentage of patients with a confirmed investigator-assessed response of complete response (CR) or partial response (PR) from the date of re-initiation of treatment with durvalumab monotherapy. ORR will be assessed in the response evaluable analysis set (patients who are retreated with durvalumab in Cohort 2).

A confirmed response of CR/PR means that a response of CR/PR is recorded at one visit and confirmed by repeat imaging not less than 4 weeks after the visit when the response was first observed with no evidence of progression between the initial and CR/PR confirmation visit. Data obtained up until progression, or last evaluable assessment in the absence of progression, will be included in the assessment of ORR. Patients who discontinue treatment without progression, receive a subsequent anticancer therapy (note that for this analysis radiotherapy is not considered a subsequent anticancer therapy) and then respond will not be included as responders in the ORR (i.e., both visits contributing to a response must be prior to subsequent therapy for the patient to be considered as a responder).

In the case where a patient has two non-consecutive visit responses of PR, then, as long as the time between the 2 visits of PR is greater than 4 weeks and there is no PD between the PR visits, the patient will be defined as a responder. Similarly, if a patient has visit responses of CR- Not evaluable (NE), CR, then, as long as the time between the 2 visits of CR is greater than 4 weeks, then a best response of CR will be assigned.

CR and PR can be assessed using the following Electronic Case Report Form (eCRF) modules:

- **Overall Exam Assessment (OVERALL):**
 - Overall Assessment of Target and Non-Target Lesions**
 - Assess Target Lesions as a Whole (CR; PR; PD; Stable Disease [SD]/ Not Evaluable)
 - Assess Non-Target Lesions as a Whole (CR/PD/ Non-CR/Non-PD; Not Evaluable)
 - Overall Tumor Response Assessment (CR; PR; PD; SD; NED); Not Evaluable
 - Latest Scan Date for the Timepoint
 - Progression Scan Date

- **Tumor Evaluation: New Lesions and Investigator Assessment of Response (RECIST2)**

Overall visit response

- RECIST response (CR; PR; PD; SD(Non-CR/Non-PD); Not evaluable)
- Investigator's opinion agrees with RECIST response (yes/no)
- Investigator's opinion of patient status (Responding; Stable; Progressing)

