3.1.2.1 Time to response (TTR)

TTR will be used in support to the DOR endpoint and will be assessed in the response evaluable analysis set (patients who are retreated with durvalumab in Cohort 2).

TTR is defined as the time from the date of first retreatment dose until the date of first documented response (CR or PR), which is subsequently confirmed.

TTR will be calculated as follows: date of documented response (CR or PR) – date of first retreatment dose +1. The date of first documented response will coincide with that used for the DOR endpoint. TTR will be expressed in months.

TTR will not be defined for those patients who do not have a documented response (CR/PR) that is subsequently confirmed.

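### The Kaplan-Meier curve for time to response (SAP 5.2.4) censors patients who can no longer respond, so it can overstate response and show a median when fewer than half respond

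*SAP*

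**What the plan says.** SAP 3.1.2.1 introduces TTR as a supportive variable: "TTR will be used in support to the DOR endpoint". It is assessed in the response evaluable set, which is every Cohort 2 patient retreated with durvalumab. The clock starts at the first retreatment dose and stops at the first response that is later confirmed. The section adds: "TTR will not be defined for those patients who do not have a documented response (CR/PR) that is subsequently confirmed".

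SAP 5.2.4 plans two displays. One is a descriptive summary in responding patients. The other is a Kaplan-Meier curve over the whole set: "KM plots of TTR will be produced where patients without a response will be censored at their last RECIST assessment". From it, "Median TTR (with associated 95% CI) will be calculated from the KM curve and summarized". If the retreated sample is too small, the tables and graphs are informative only; no threshold is given.

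SAP 3.1.1 fixes when a response can still count. "Data obtained up until progression, or last evaluable assessment in the absence of progression, will be included in the assessment of ORR", and for subsequent anticancer therapy (radiotherapy excepted) "both visits contributing to a response must be prior to subsequent therapy for the patient to be considered as a responder".

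On scanning during retreatment, Protocol Table 2 has RECIST assessment "as determined by the Investigator (at least every 12 weeks) until withdrawal of consent, progression or death". Protocol 1.1 adds: "There are no mandated confirmatory scans, unless the Investigator plans to treat the patient beyond PD".

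**The concern.** Kaplan-Meier censoring assumes that a censored patient remains as likely to respond later as those still being followed. That is reasonable for a patient without progression at data cut-off. It is false for a patient who has progressed, died or begun another therapy, because SAP 3.1.1 rules out a later response. These are competing events, and removing such patients from the risk set inflates every later step of the curve.

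At stake is a reported median TTR with a CI, in the only population with ORR and DOR analyses, that can imply at least half of patients respond while the ORR table for the same patients shows fewer.

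**Working it through.** The documents give no retreated sample size, response rate or progression rate, so there is no planned figure to reproduce. All counts below are assumed.

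**Direction.** Give each of n patients mass 1/n. Kaplan-Meier passes the mass of each censored patient to those still at risk. Each of the r responders therefore ends with at least 1/n, and the plateau of 1-KM is at least r/n, the ORR. Equality holds only if no non-responder is censored before the last response. A check on 200,000 random data sets (those without a response skipped) found no exception to either statement. Both concern the plateau; early in time the curve lies below the final ORR.

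**Two examples, n = 40, three scans.** Formula: 1-KM = 1 - product of (1 - responses / at risk). Non-responders are first censored at the progression scan, then at one scan later.

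| | Responses / at risk | 1-KM | ORR (exact 95% CI) |
|---|---|---|---|
| A, progression scan last | 6/40, 3/18, 1/7 | 1 - (34/40)(15/18)(6/7) = 39% | 10/40 = 25% (12.7 to 41.2%) |
| A, one further scan | 6/40, 3/34, 1/15 | 1 - (34/40)(31/34)(14/15) = 28% | same |
| B, progression scan last | 8/40, 4/16, 2/5 | 1 - (0.80)(0.75)(0.60) = 64% | 14/40 = 35% (20.6 to 51.7%) |
| B, one further scan | 8/40, 4/32, 2/12 | 1 - (32/40)(28/32)(10/12) = 42% | same |

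In B with the progression scan last, the curve reads 20%, 40% and 64%, so a median is reported at the third scan although 35% responded. With one further scan there is no median. A cumulative incidence curve with the non-responders as competing events ends at 25% in A and 35% in B under either scan pattern.

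**How typical.** Assumptions: first response at scan 1, 2 or 3 with probability 0.6, 0.3, 0.1; non-responders progress with probability 0.4 or 0.6 per scan; n = 20, 40, 80; 4,000 runs per setting. No patient is censored at data cut-off, so all the excess here is competing-event bias.

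| True ORR | Mean 1-KM, progression scan last | Mean 1-KM, one further scan |
|---|---|---|
| 15% | 20 to 27% | 16 to 17% |
| 25% | 33 to 43% | 27 to 29% |
| 35% | 45 to 56% | 37 to 40% |

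At n = 40 and ORR 35%, a median with under half responding appears in about 26 to 63% of runs, or 3 to 10% with one further scan. Example B is at the high end: 1-KM reaches 64% in about 2 to 29% of runs.

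**Separating bias from ordinary censoring.** Take n = 20. At scan 1 there are 5 responses, 5 progressions and 6 event-free patients with no later scan. At scan 2, 4 are at risk, with 2 responses and 2 progressions.
- ORR = 7/20 = 35%.
- 1-KM = 1 - (15/20)(2/4) = 62.5%.
- Aalen-Johansen cumulative incidence = 5/20 + (10/20)(2/4) = 50%.

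Of the 27.5-point excess of 1-KM over ORR, 62.5 - 50 = 12.5 points are competing-event bias. The other 50 - 35 = 15 points come from ordinary censoring of event-free patients.

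**No scan on retreatment.** Protocol 6.1.3 allows the retreatment baseline scan up to 28 days before restarting. If that is the last assessment, the censoring time on the SAP's TTR scale is -28 + 1 = -27 days, before the clock starts. SAP 5.2.4 gives no rule for this.

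**The case against.** The strongest defence is that little depends on the curve. TTR is not among the endpoints in the protocol's Table 4 or SAP Table 1. SAP 5.1 plans no hypothesis test, the ORR with its exact CI is reported for the same patients, and a responder-only summary is already planned and unaffected. The KM display is informative only if the sample is small. All of this stands and limits the point to a minor one.

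The defence is also right that crude ORR is an imperfect benchmark. SAP 5.2.4 censors everyone without a response, including patients still on retreatment without progression. For them a curve above the ORR is a legitimate adjustment for incomplete follow-up. A reader might infer that the whole gap is bias; the 20-patient example shows that it need not be.

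Treatment beyond progression is allowed and can bring later scans, which delays censoring. This shrinks the excess but cannot reverse it.

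A reader might also infer that SAP 3.1.2.1 and 5.2.4 contradict each other, since TTR is undefined without a confirmed response yet non-responders enter the curve. The documents do not support that. Section 3.1.2.1 itself places TTR in the full response evaluable set, and a censored patient has no observed TTR value, so the two can be read together. At most this is an inconsistency of presentation. The competing-event argument does not need it.

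**Conclusion.** The point holds as a minor flaw in a supportive analysis. For patients who have progressed, died or started subsequent anticancer therapy, censoring in the TTR curve is inappropriate under the SAP's own response rules and biases 1-KM upward. A KM median can then be reported when fewer than half respond.

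The direction follows from algebra and needs no assumption about rates. The size is unknown. It depends on how early non-responders leave, on how often scans continue after progression, and on the number retreated. In the assumed 40-patient example B it ranges from 7 points (42% against 35%) to 29 points (64% against 35%). No conclusion on ORR, DOR or safety is affected.

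**What to change.** In SAP 5.2.4, report median TTR only in the descriptive summary of confirmed responders; SAP 5.1 already includes the median in such summaries. Then do one of the following.

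1. Delete the KM plot and its median. This is enough, and it is the only option that guarantees no whole-set median alongside an ORR below 50%.
2. Replace them with a cumulative incidence (Aalen-Johansen) curve. Competing events are progression, death and subsequent anticancer therapy, with radiotherapy excepted as in SAP 3.1.1. Censor only patients who are event-free at data cut-off, withdrawal of consent or loss to follow-up, at their last evaluable RECIST assessment, or at Day 1 if they have no scan on retreatment.

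Option 2 removes the competing-event bias. Because event-free patients are still censored, the curve can still differ from the crude ORR and can reach 50% when fewer respond, as in the 20-patient example. A footnote should say so.

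The cost is a few lines of SAP text, slight extra programming with standard software for option 2, and a less favourable-looking curve.

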5.2.5 Safety

Safety data will be summarized according to the treatment received for the SAS (all patients who received at least 1 dose of durvalumab either as continuation of study treatment or retreatment in this study, and inclusive of patients who received the last dose of durvalumab or durvalumab combination from the parent clinical study within 90 days of enrollment [all cohorts]). AEs, vital signs, dose at time of AE, and laboratory safety assessments (clinical chemistry, hematology and thyroid stimulating hormone [reflex free triiodothyronine or free thyroxine]) will be listed individually by patient.

The number of patients experiencing each AE will be summarized by study cohort and CTCAE grade (v5.0). Each patient will be represented with the maximum reported CTCAE grade for each system organ class / preferred term. Number (%) of patients with AEs, will be sorted by international System Organ Classes (SOC) order and alphabetical PT and then maximum grade. Event rate per 100 patient-years will also be calculated for each AE.

Individual laboratory measurements and vital signs data will be presented in listing format.

For laboratory measurements, the following data will be listed:

- Subject identifier and cohort
- Age/sex/race
- Analysis visit
- Category of lab test
- Lab test examination name

- Result/finding
- Units
- Reference range indicator

For vital signs, the following data will be listed:

- Subject identifier and cohort
- Vital signs test name
- Analysis visit
- Result
- Unit
- Result clinically significant (yes/no)
- Reference ranges (upper and lower limits).

For vital signs, the following reference ranges and units will be used:

- For Diastolic blood pressure: Range = 40-110, Unit = mmHg
- For Heart rate/Pulse: Range = 50-120, Unit = beats/min
- For Respiratory rate: Range = 12-35, Unit = breaths/min
- For Systolic blood pressure: Range = 60-160, Unit = mmHg
- For Temperature: Range = 35-39, Unit = °C / Range = 95-102.3, Unit = °F
- For Weight: Range = 30-140, Unit = Kg / Range = 66-308, Unit = LB
- Oxygen saturation: 95-100%, unit-free.

Note: Based on an “as needed” request from parent clinical studies, safety data from WAVE may be combined with parent study data in order to update safety summaries.

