6.1 Treatments administered

6.1.1 Investigational product

AstraZeneca will supply durvalumab (MEDI4736). All patients in Cohort 1 will receive durvalumab monotherapy at the dosing regimen described below (Table 6). While patients in Cohort 2 are all eligible for retreatment with durvalumab, some may never receive treatment. Patients who were previously administered durvalumab at a dose regimen different from the regimen described for the present study will switch to the dose regimen described below. Only 1 course of retreatment is allowed (inclusive of any retreatment in the parent clinical study). Patients enrolled in Cohort 3 will not receive any study drug.

Table 6 Study treatment

	Treatment
Study treatment name:	Durvalumab (MEDI4736)
Dosage formulation:	500-mg vial solution for infusion after dilution, 50 mg/mL
Route of administration:	Intravenous (IV)
Dose:	1500 mg
Dosing instructions:	A dose of 1500 mg will be delivered through an IV administration set with a 0.2 µm or 0.22 µm filter. If a patient’s weight falls to 30 kg or below (≤ 30 kg), then the patient should receive weight-based dosing equivalent to 20 mg/kg of durvalumab q4w until weight improves to above 30 kg (>30 kg).
Packaging and labeling:	Study drug will be provided in vials. Each vial will be labeled in accordance with Good Manufacturing Practice Annex 13 and per country regulatory requirement. ^a
Frequency:	Every 4 weeks
Manufacturer:	MedImmune
Provider:	AstraZeneca

^a Label text prepared for durvalumab (MEDI4736) will show the product name as “MEDI4736” or “durvalumab (MEDI4736)” depending upon the agreed product name used in the approved study master label document. All naming conventions are correct during this transitional period.

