8. STUDY ASSESSMENTS AND PROCEDURES

Data collection and frequency are summarized by each of the 3 cohorts below:

In Cohort 1, all durvalumab treatment cycle assessments will occur every 4 weeks until confirmed PD, unless unacceptable toxicity, withdrawal of consent, or another discontinuation criterion is met. The most recent imaging results from the parent clinical study may be used for baseline tumor assessments, provided it was obtained within 28 days prior to Day 1, Cycle 1. Tumor assessments throughout all cycles will be performed according to RECIST v1.1, as determined by the Investigator (at least every 12 weeks) until withdrawal of consent, progression, or death. The patients will continue their durvalumab treatment and all cycle assessments every 4 weeks ± 3 days unless dosing needs to be held for toxicity reasons ([Table 1](#)).

Cohort 2 follow-up prior to retreatment with durvalumab monotherapy follows the SoA for Cohort 3, while patients who undergo retreatment begin the assessment as per the SoA for patients in Cohort 1. During the follow-up of patients before retreatment, they will undergo assessments for vital signs, concomitant medications, laboratory safety and AE/SAE at 30 days (± 3 days), 60 days (± 7 days), and 90 days (± 7 days) since the last dose of study drug. The assessment for concomitant medications will be collected throughout 90 days post durvalumab discontinuation. The survival status for these patients will be collected every 3 months (± 2 weeks) beginning 90 days after the last dose of the study drug and tumor assessments will be performed according to the Investigator's standard practice until withdrawal of consent, progression, or death. For those that start retreatment, patients will continue their durvalumab monotherapy and all cycle assessments every 4 weeks ± 3 days unless dosing needs to be held for toxicity reasons. While on retreatment, tumor assessments and disease progression will be determined by the Investigator following RECIST v1.1 ([Table 2](#)).

Cohort 3 includes safety and survival follow-up only for patients previously treated with durvalumab monotherapy or durvalumab in combination with any other approved or investigational anticancer agents who are no longer receiving durvalumab and are not eligible to receive retreatment. The patients would undergo assessments as per the SoA (Table 3).

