2.1.2 Response evaluable analysis set

The response evaluable analysis set will consist of patients who are retreated with durvalumab in Cohort 2. This will be the analysis set for ORR and DOR.

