2.1.3 Safety Analysis Set (SAS)

The SAS will consist of patients who received at least 1 dose of durvalumab on this study or enrolled on this study within 90 days of the last dose of durvalumab or durvalumab combination on the respective parent clinical study. The primary objective analysis will be assessed in the SAS.

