- Must not have required the use of additional immunosuppression other than corticosteroids for the management of an AE >Grade 1, have not experienced recurrence of an AE if re-challenged, and not currently require maintenance doses of >10 mg prednisone or equivalent per day
- Known allergy or hypersensitivity to any of the study drugs or any of the study drug excipients
- **Deviation 2:** Baseline RECIST scan date is greater than 28 days before the date of starting Cycle 1 of retreatment for Cohort 2, during the WAVE study period.
- **Deviation 3:** No baseline RECIST 1.1 assessment on or before the date of starting Cycle 1 of retreatment (Cohort 2), during the WAVE study period.
- **Deviation 4:** Received prohibited concomitant medications (including other anticancer agents). Please refer to the CSP Section 6.4 for those medications that are detailed as being ‘excluded’ from permitted use during the study. This will be used as a guiding principle for the medical data reviewer of all medications prior to database lock.

All the violations and deviations considered only come from WAVE without taking into account data from parent studies. The important subject-level protocol deviations will be listed and summarized by treatment group (study cohort) in the main part of the CSR. All

participants with important protocol deviations will be listed by center, as an appendix. Site level protocol deviations are collected from the CTMS. The important site level protocol deviations will be listed, as an appendix of the CSR.

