5.2.6 Demographics and baseline characteristics

The following will be summarized for all patients in the FAS by treatment group (cohort 1, cohort 2, cohort 3). Continuous variables will be summarized by the number of observations, mean, Sd, median, upper and lower quartiles minimum, and maximum. Categorical variables will be summarized by frequency counts and percentages for each category:

- Patient disposition (including screening failures) and inclusion in analysis sets
- Demographics (age, age group [<50 , $\geq 50 - < 65$, $\geq 65 - < 75$ and ≥ 75 years], sex, race, ethnicity, and country)
- Subject recruitment by clinical parent study (for each parent study; the study design, code, total number of patients in parent study and in WAVE study)
- Patient recruitment by country and by center

- Patient characteristics at baseline (height, weight, BMI)
- Disease characteristics at baseline (ECOG performance status, primary tumor location)
- Extent of disease at baseline: locally advanced/metastatic, site of disease

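### Tabulating AEs by study cohort can put retreated and never-retreated Cohort 2 patients into one percentage, although their scheduled AE follow-up differs

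*SAP*

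**What the plan says.** SAP 5.2.5 sets the grouping of the AE incidence table: "The number of patients experiencing each AE will be summarized by study cohort and CTCAE grade (v5.0". Protocol 9.3.1 plans the same table. The section opens by saying that safety data follow the treatment received. It also plans patient listings of AEs with the dose at the time, and an event rate per 100 patient-years.

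SAP 2.1.3 admits a patient to the safety set in either of two ways: the patient "received at least 1 dose of durvalumab on this study or enrolled on this study within 90 days of the last dose of durvalumab" (or of a durvalumab combination) in the parent study. SAP 5.2.5 applies this to all cohorts.

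Protocol 6.1.1 says of Cohort 2: "While patients in Cohort 2 are all eligible for retreatment with durvalumab, some may never receive treatment". Before retreatment, Protocol section 8 says "they will undergo assessments for vital signs, concomitant medications, laboratory safety and AE/SAE at 30 days", with further visits at days 60 and 90 after the last dose. Footnote a to Table 2 in Protocol 1.1 then closes the schedule: "Patients who are more than 90 days beyond the last dose of study drug, will not undergo follow-up for AEs/SAEs". Retreated patients have AE assessment throughout an open-ended course and for 90 days after its last dose.

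Elsewhere the SAP does isolate retreated patients. Section 2.1.2 reads: "The response evaluable analysis set will consist of patients who are retreated with durvalumab in Cohort 2". Section 5.2.8 limits the exposure summary to Cohort 1 and the retreated part of Cohort 2.

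**The concern.** Long-term safety is the primary objective, and retreatment is one of only two ways in which durvalumab is given in WAVE. A reader of the AE table will want to know how often events occurred in patients who restarted the drug. If the Cohort 2 column also holds patients who were only observed for the tail of their parent-study follow-up, its n (%) describes neither group. The exposure table and the AE table for Cohort 2 would also rest on different sets of patients.

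**Working it through.** The plan states no figure on this point, so there is none to reproduce. The check traces who can be in the column, then compares the scheduled AE windows.

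**Who can be in the Cohort 2 column**

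| Cohort 2 patient | In the safety set? | Source |
|---|---|---|
| Retreated in WAVE | Yes, through a WAVE dose | SAP 2.1.3 |
| Never retreated, enrolled within 90 days of last parent dose | Yes, through the enrollment route | SAP 2.1.3, 5.2.5 |
| Never retreated, enrolled later | No | SAP 2.1.3 |

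The first two rows share a column. The third row bounds the pooling. SAP 5.1 takes percentages out of the analysis-set total unless otherwise stated, and nothing in 5.2.5 makes the denominator depend on retreatment.

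**Does the reference to treatment received supply the split?** Section 5.2.5 defines no treatment categories for the AE table, and its sentence on AE counts names cohort and grade. Where the SAP speaks of a treatment group, it means cohort: "listed and summarized by treatment group (study cohort) in the main part of the CSR" in 2.2 and "by treatment group (cohort 1, cohort 2, cohort 3" in 5.2.6. Those two uses concern deviations and FAS demographics, not the safety set, so they are suggestive and not decisive.

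**Scheduled AE windows** (days, counted inclusively)

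Inputs: dosing every 28 days (Protocol 6.1.2.1), and AE collection from consent to 90 days after the last dose (Protocol 8.3.2). Dose delays, death, withdrawal and data cut-off are ignored.

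- Retreated, n infusions, from first WAVE dose to last WAVE dose + 90: W = 28(n-1) + 91.
- Never retreated, enrolled d days after the last parent dose: U = 91 - d.
- Difference: W - U = 28(n-1) + d. With n at least 1 and d at least 0, this is never negative.

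The values of n and d below are assumptions, chosen to show the range.

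| n | d | W | U | W - U |
|---|---|---|---|---|
| 1 | 0 | 91 | 91 | 0 |
| 3 | 0 | 147 | 91 | 56 |
| 6 | 45 | 231 | 46 | 185 |
| 12 | 60 | 399 | 31 | 368 |

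Turning days into percentages would need AE rates and the retreated share of the column. The documents give neither, so no dilution is estimated.

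**Patient-time (secondary).** SAP 5.2.5 does not name the denominator of the event rate. The on-treatment window in SAP 3.2.1 starts at first dose. For a patient not dosed in WAVE that dose lies in the parent study, whereas WAVE collects AEs only from consent.

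**The case against.** **Treatment received may already be the split.** The opening sentence of 5.2.5 goes on to mention continuation, retreatment and a recent parent-study dose, and 5.2.8 already uses a retreated Cohort 2 group within the safety set. A programmer could build sub-columns from that. No table shell is in the documents, and tabulating by cohort does not forbid sub-columns. This stands in part: the text is ambiguous. A reader might infer that the plan rules out a split, but the documents only fail to ask for one clearly.

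**The direction is not established.** A reader might infer that the pooled figure must understate AEs in retreated patients. Window length gives that result only if daily risk is similar. Never-retreated patients in the safety set are within 90 days of parent dosing, which may have been combination therapy, so either group could have the higher daily rate. This stands in full.

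**Much is already covered.** No hypothesis is tested, AEs and dose at the time are listed by patient, retreated exposure is summarized separately, and an event rate is planned. A retreated-only count could be assembled by hand. This limits the consequence. But the rate adjusts only in part for unequal follow-up and does not separate the groups, and neither it nor the listings changes the n (%).

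**The by-cohort table is the protocol's own plan, and the safety objective covers all cohorts.** True, but keeping the cohort columns does not prevent dividing one of them.

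**Conclusion.** The point holds as a cheap improvement. As written, the Cohort 2 n (%) can combine patients retreated in WAVE with never-retreated patients who enrolled within 90 days of their last parent dose. On schedule the retreated AE window is longer by 28(n-1)+d days.

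Understatement of AE incidence in retreated patients follows only on the assumption that daily AE risk is similar in the two groups. Otherwise the direction is unknown. The size is also unknown: it is small or nil if few never-retreated patients enrolled within 90 days. The difference in days should not be read as an estimate of bias in the percentage. Nor should a reader infer that every never-retreated Cohort 2 patient dilutes the column, since those who enrolled after day 90 are outside the safety set.

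**What to change.** In SAP 5.2.5, split the Cohort 2 AE column, or add a supplementary CSR table if outputs are already final.

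- **(a) Retreated.** AEs starting or worsening from first WAVE dose to last WAVE dose + 90 days. N = retreated patients.
- **(b) Before or without retreatment.** AEs starting or worsening from WAVE enrollment to the earlier of last parent dose + 90 days and first WAVE dose. N = Cohort 2 patients enrolled within 90 days of the last parent dose.
- State that a patient may count in both columns, over non-overlapping periods.
- State that AEs outside both windows are listed and counted separately, so that no collected AE drops out. These are events after last parent dose + 90 days but before first WAVE dose (for example, between re-consent and first infusion), and late-onset events after day 90, which Protocol 8.3.2 still allows to be reported.
- Define patient-years for each column as its own observation window, also ending at death, withdrawal or data cut-off.

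The cost is SAP wording and one extra column, with smaller denominators in each. No new data are needed: SAP section 4 shows the parent last-dose date as an EDC entry and WAVE dosing dates in the exposure module.
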